8.4.4 Other safety evaluations

Renal function

Renal function will be assessed at each visit by measuring serum creatinine and utilized to calculate the estimated glomerular filtration rate (eGFR) using the MDRD-4 formula.

New onset diabetes mellitus

New onset diabetes mellitus is defined as:

All of the following should be true (no diabetes mellitus pre-transplantation):

- Diabetes was not included in the medical history.
- Glucose (random) <11.1 mmol/L (200 mg/dL) at the time of transplantation.
- Diabetes was not recorded as reason for any medication given prior to transplantation.
- HbA1c <5.7% at the time of transplantation.

And at least one of the following should be true (diabetes onset after randomization):

- Two consecutive fasting plasma glucose (FPG) ≥126 mg/dL (7.0 mmol/L) at any time after Day 29 or a random plasma glucose (RPG) ≥200 mg/dL (11.1 mmol/L).
- HbA1c \geq 6.5% (only from Day 85 forward).
- Diabetes reported as an AE that is prevalent after Day 29.
- Any concomitant medication with Anatomical Therapeutic Chemical (ATC) level 2 code "A10" (drugs used in diabetes), if prevalent after Day 29.

Definitions for diabetic related diagnoses are according to the American Diabetes Association 2013 and [WHO-ADA criteria].

Hepatic Artery Thrombosis

Hepatic Artery Thrombosis (HAT) are frequent in this population and will be recorded as Adverse Events or Serious Adverse Events as appropriate. The treatments given should be recorded on the Concomitant Medications and/or the Surgical and Medical Procedures CRF (e.g., re-anastomosis, stent, etc.) as appropriate.

Malignancies

For participants on study treatment and in follow-up, any type of malignancy (including skin neoplasms, leukemia, post-transplantation proliferative disorder (PTLD)) should be reported as a SAE and recorded on the appropriate CRFs. A SAE report should be completed for malignancies occurring until the last visit (for participants in follow-up) or for 14 weeks after the last dose of study treatment taken, (for participants in the treatment period or who completed the treatment period).

Hepatocellular carcinoma (HCC) recurrence

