12.5.2.2 General safety

For all other safety analyses, the safety set will be used. Adverse events (AEs) will be presented and summarized for all treatment-emergent events, with a start date after randomization, whether on- or off-treatment. In addition, a separate summary for death including on treatment and post treatment deaths will be provided. General safety summaries (tables, figures) will

Novartis	Confidential	Page 115 of 136
Amended Clinical Trial Protocol (Version No.	04 clean)	Protocol No. CCFZ533A2202

include only data from the on-treatment period with the exception of baseline data which will also be summarized where appropriate (e.g. change from baseline summaries).

For CFZ533, the on-treatment period lasts from the date of first administration of study treatment to 14 days after the date of the last actual administration. For TAC, it lasts to the day of the last actual administration.

Adverse events

All information obtained on adverse events will be displayed by treatment group.

The number and percentage of participants with treatment emergent adverse events and serious adverse events (events started after the first dose of study medication or events present prior to start of treatment but increased in severity based on preferred term) will be summarized in the following ways:

- by treatment, primary system organ class and preferred term.
- by treatment, primary system organ class, preferred term and maximum severity by treatment, Standardized MedDRA Query (SMQ) and preferred term.

Separate summaries will be provided for study medication related adverse events, death, serious adverse events, other significant adverse events leading to discontinuation and adverse events leading to dose adjustment.

In addition, the proportion of participants with infections will be summarized as follows:

- 1. Infections by type of infection (viral, fungal, bacterial, others) and microorganism of infection
- 2. Serious infections by type of infection (viral, fungal, bacterial, others) and microorganism of infection

The incidence rate of infection by type and micro-organism will be tabulated for each treatment arm. The key safety parameter is serious infections. The number of serious infections will be used to evaluate the stopping rule as outlined in Section 9.1.5.

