2.1.2 Analysis sets

The screened set (SCR) consists of all participants who signed the informed consent. The screened set includes only uniquely screened participants, i.e., in the case of re-screened participants, only the chronologically last screened data is counted. Screening phase disposition will be based on the SCR.

The randomized set (RND) consists of all participants who signed the informed consent and were randomized, including misrandomizations.

The full analysis set (FAS) will include all participants who were transplanted and randomized, excluding mis-randomized participants. Mis-randomized participants are defined as cases where IRT contacts were made by the Investigator/qualified site staff either prematurely or inappropriately to confirmation of the participant's final randomization eligibility and treatment was not administered to the participant. Following the intention-to-treat (ITT) principle, participants will be analyzed according to their treatment assignment at randomization. Participant demographics, baseline characteristics, efficacy and renal function measured by GFR will be performed on the FAS.

The safety set (SAF) consists of all participants in FAS who received at least one dose of study drug (i.e., at least one dose of TAC after randomization in the Control arm and at least one dose of CFZ533 in the CFZ533 arms). Participants will be analyzed according to the treatment they actually received. All safety analyses, including renal function parameters other than GFR, will be performed on the SAF using on-treatment (between start and end of treatment defined in Section 2.1.1) data unless otherwise specified.

The PK analysis set (PKS) will include all participants with at least one available valid (i.e., not flagged for exclusion) PK concentration measurement, who received any study drug and with no protocol deviations that impact on PK data, e.g. if a dose was taken more than 7 days after the planned date.

The total screened participants and each analysis population above will be summarized in terms of the frequencies and percentages. Listings of randomized participants and of the participants excluded from analysis sets will be provided.

Rules for exclusion from analysis sets is in Table 5-9.

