2.7 Safety analyses

The SAF will be used for safety analyses unless otherwise specified. General safety summaries (tables, figures, etc.) will include only data from the on-treatment period with the exception of baseline data which will also be summarized where appropriate (e.g., change from baseline summaries), unless otherwise specified. For CFZ533 arms, the on-treatment period lasts from the date of first administration of study treatment to 14 days after the date of the last actual administration. For the Control arm, it lasts to the day of the last actual administration of TAC.

Adverse events (AEs) will be presented and summarized for all treatment-emergent events, with a start date after randomization and covering until 14 weeks after the last administration of CFZ533 for CFZ533 arms and 12 weeks after that of TAC for TAC arm. In addition, a separate summary for death will be provided. Malignancies are summarized under SAEs.

All information obtained on adverse events will be displayed by treatment group. The number and percentage of participants with treatment-emergent adverse events and serious adverse events (events started after the first dose of study medication or events present prior to start of treatment but increased in severity based on preferred term) will be summarized in the following ways:

- by treatment, primary system organ class and/or preferred term
- by treatment, primary system organ class, preferred term and/or maximum severity

Separate summaries will be provided for AEs leading to treatment discontinuation.

In addition, the proportion of participants with infections will be summarized as follows:

- Infections by type of infection (viral, fungal, bacterial, others) and severity.
- Serious infections by type of infection (viral, fungal, bacterial, others) and severity.

The incidence rate of infection by type (viral, bacterial, fungal, and others) will be tabulated for each treatment arm. The key safety parameter is serious infections. The number of serious infections will be used to evaluate the stopping rule as outlined in Section 9.1.5 in Protocol.

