2.7.2 Deaths

In addition to the output required for disclosure, the number of deaths will be tabulated by treatment.

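### SAP 2.7 ends the AE and SAE tables, malignancies included, 14 or 12 weeks after last dose and leaves the death table without a window, although the protocol summarises off-treatment events and post-treatment deaths

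*SAP*

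**What the plan says.** **Protocol.** Section 12.5.2.2 summarises treatment-emergent adverse events "with a start date after randomization, whether on- or off-treatment", and adds that "a separate summary for death including on treatment and post treatment deaths will be provided". The same section restricts general safety summaries to on-treatment data. Section 8 keeps randomised participants in the study to Month 24 after they stop treatment. Section 8.4.4 states: "A SAE report should be completed for malignancies occurring until the last visit (for participants in follow-up". For people in the treatment period, or who completed it, the malignancy reporting limit is 14 weeks after last dose.

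**SAP.** Section 2.7 summarises AEs that start after randomisation, "covering until 14 weeks after the last administration of CFZ533 for CFZ533 arms and 12 weeks after that of TAC for TAC arm". It then announces a separate death summary, without the protocol's mention of post-treatment deaths, and says "Malignancies are summarized under SAEs". Section 2.7.2 adds only that, beyond the disclosure output, "the number of deaths will be tabulated by treatment".

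The SAP default appears twice. Section 2.1.2 has "All safety analyses, including renal function parameters other than GFR, will be performed on the SAF using on-treatment" data, and section 2.7 has "General safety summaries (tables, figures, etc.) will include only data from the on-treatment period", in each case unless another rule is given. On-treatment ends 14 days after the last CFZ533 dose and on the day of the last TAC dose.

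Two further rules bear on the same events. SAP 2.1 bases AE, SAE and malignancy summaries on every eligible event collected, without defining eligible, and says listings show everything available. SAP 5.5.1 censors exposure-adjusted rates at the earlier of the end of observation and EOT. SAP section 4, on changes from the protocol, is marked not applicable.

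**The concern.** The protocol keeps people under observation off treatment and asks for malignancies and survival status during that time. The SAP then stops counting malignancies in the by-arm tables a few months after last dose, and no longer says that post-treatment deaths are counted.

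These are rare, serious outcomes. Protocol 4.6 lists lymphoproliferative disorders as a potential risk, and SAP Table 2-2 makes malignancy, lymphoproliferative disorder included, a safety topic of interest. With planned arms of 32 and 48, a single event is 1/32 = 3.1 or 1/48 = 2.1 percentage points, so omitting one or two can change how a table reads.

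The study was terminated because risk-benefit was no longer favourable (SAP section 1), so the abbreviated report becomes the main safety record. A programmer following the SAP could use the 14/12-week window, all eligible events, or censoring at EOT, and each gives different counts or rates.

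**Working it through.** The documents give no figure to reproduce; this is window arithmetic.

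**Inputs**
- Randomisation at Day 8 and Month 24 at Day 673 (Protocol Tables 8-1 and 8-2), so post-randomisation time is 673 − 8 = 665 days.
- AE/SAE window (SAP 2.7): 14 × 7 = 98 days for CFZ533, 12 × 7 = 84 days for TAC.
- On-treatment default (SAP 2.7): 14 days for CFZ533, 0 days for TAC.
- Stop days 85 and 169 are assumptions. The documents give no discontinuation rates or times.

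**Step 1: malignancies outside the SAE tables, followed to Day 673**

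Uncovered days = 673 − (stop day + window).

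| Last dose | Arm | Window ends | Uncovered days | Share of 665 |
|---|---|---|---|---|
| Day 85 | CFZ533 | 85 + 98 = 183 | 673 − 183 = 490 | 74% |
| Day 85 | TAC | 85 + 84 = 169 | 673 − 169 = 504 | 76% |
| Day 169 | CFZ533 | 169 + 98 = 267 | 673 − 267 = 406 | 61% |
| Day 169 | TAC | 169 + 84 = 253 | 673 − 253 = 420 | 63% |

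Under the protocol's rule the uncovered time is 0 days in every arm.

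**Step 2: shorter horizon.** Taken only to Month 12 (Day 337), and as a share of off-treatment time, a stop at Day 169 leaves (168 − 98)/168 = 41.7% uncovered on CFZ533 and (168 − 84)/168 = 50.0% on TAC. A stop at Day 29 leaves (308 − 98)/308 = 68.2% and (308 − 84)/308 = 72.7%.

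**Step 3: deaths, only if the default is applied.** For a stop at Day 169, off-treatment follow-up to Day 673 is 504 days. Uncovered: 504 − 14 = 490 days (97.2%) on CFZ533 and 504 − 0 = 504 days (100%) on TAC.

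**Step 4: do the windows themselves favour an arm?** Protocol 4.2.1 puts the last CFZ533 dose before Month 24 at Day 659, and 659 + 98 = 757. A control participant whose last TAC dose is at Day 673 reaches 673 + 84 = 757. The difference of 98 − 84 = 14 days is the CFZ533 dosing interval. At a common stop day, control loses 14 days more.

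**Step 5: how much follow-up could exist?** The study was terminated in September 2022. Twenty participants had been randomised by 30 July 2020 (Amendment 03), and 665 days after that date is 26 May 2022. Those still followed could therefore have reached Day 673. By 28 February 2021, 59 had been randomised (Amendment 04), about 18 months before termination. The Month 24 figures are upper bounds, but not empty ones.

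**The case against.** **The window has a basis in the protocol.** Fourteen and 12 weeks match the safety follow-up in Protocol 9.2 and the SAE reporting period in 10.1.3, and Protocol 4.2.1 expects no pharmacodynamic activity in target tissues beyond about 14 weeks. This stands as a reason for the window in general AE tables. It does not answer 8.4.4, which collects malignancies to the last visit off treatment, or 12.5.2.2, which counts off-treatment events.

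**A reader might infer that late events vanish.** They do not. SAP listings contain all available data. Deaths also appear among the summarised components of the composite (SAP 2.4.5), where the Kaplan-Meier analysis follows people past discontinuation to last contact, within Month 12. SAP Table 2-2 plans a malignancy topic summary with no window of its own. These routes are partial: the primary Poisson analysis ends follow-up at treatment discontinuation (SAP 2.4.2), the Kaplan-Meier analysis stops at Month 12, and listings give no by-arm rates.

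**A reader might infer that the SAP cuts deaths at 14 or 0 days.** It does not say so. Section 2.7.2 has no window, and the cut follows only if the default is read into it.

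**A reader might infer that the loss is unequal by arm**, for example 74% for someone who stops CFZ533 early against 0% for a control who stays on TAC. That compares stopping with continuing. Unequal loss needs different discontinuation rates or timing. Protocol 6.6.2 makes that plausible, since some rejection treatments end CFZ533 while more tacrolimus is a listed option for controls, but no rates are given.

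**Departures are disclosed in general terms.** SAP sections 1 and 2.1 say analyses were reduced and may differ from the protocol. That is true, but this change is not itemised, and section 4 denies any change.

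**Conclusion.** The point holds as an undeclared narrowing of the protocol's safety analysis. As SAP 2.7 is written, malignancies beyond 14 weeks (CFZ533) or 12 weeks (TAC) after last dose drop out of the by-arm SAE tables although they are collected. SAP 2.1 conflicts with that, and 5.5.1 adds a third cut-off for exposure-adjusted rates. For deaths the defect is an ambiguity: the protocol's commitment has gone and no window replaces it.

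For a participant who stops at Day 85 or Day 169 and is followed to Day 673, the SAE tables miss 61% to 76% of post-randomisation time. This rests on assumed stop days and on follow-up to Month 24, so it is an upper bound. It applies only to participants who stop early, and it measures time at risk, not lost events. Neither a between-arm bias nor an express cut on deaths is established. The correction is worth making because it restores the protocol's rule for the gravest outcomes using data already held.

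**What to change.** - In SAP 2.7 and 2.7.2, tabulate all deaths and all malignancies (including PTLD) by arm from randomisation to last contact, split into on-treatment and post-treatment.
- Keep the 14/12-week window for the general AE tables.
- Reconcile SAP 2.1, 2.7 and 5.5.1: define which events are eligible, and state which cut-off governs the counts and which the exposure-adjusted rates.
- Replace the entry in section 4 with an itemised statement of the change.

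The cost is SAP wording and two tables from data already in the database. The downside is that some events after conversion to standard of care are less attributable to study drug; the on/post split makes that visible.

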Participants transplanted for HCC or with HCC diagnosed at the time of transplantation should be monitored for HCC recurrence according to local practice. For example routine laboratory monitoring/tests, tumor markers, hepatic ultrasound, computed tomography scans (CAT, CT) or Magnetic Resonance Imaging (MRI) (especially Fe-MRI) on regular basis as per local practice. A-fetoprotein will be regularly evaluated at the central laboratory, Table 8-1, Table 8-2 and Table 8-3.

All cases of HCC recurrence or de novo HCC, diagnosed post-randomization should be recorded on the appropriate CRF. Details of method of diagnosis, location (hepatic and/or extrahepatic) of lesions, number/size of lesions, tumoral invasion of major vessels or biliary system and any treatment given should be recorded on the CRFs. In addition, a SAE report should be completed.

Novartis	Confidential	Page 93 of 136
Amended Clinical Trial Protocol (Version No.	04 clean)	Protocol No. CCFZ533A2202

In the event of HCC recurrence, the slides from the explant liver graft biopsy will be sent to the independent central pathologist for evaluation.

For recurrent and *de novo* cases of HCC, α -fetoprotein will be monitored as needed.

Dialysis

All instances of renal replacement therapy (including hemodialysis, hemodiafiltration, hemofiltration and peritoneal dialysis) occurring post transplantation should be recorded on the appropriate CRF giving the method used. Reason for dialysis, the start and end dates and the total number of sessions should also be recorded.

Infections

Infections should be recorded with start and end date, type of infection, and medications used on the CRF capturing Adverse Events. If medications are used to treat the infection, the name of the medication must be entered on the appropriate CRF. If the participant is hospitalized a SAE report must be completed and reported.

Viral infections (CMV, EBV)

Quantitative EBV and CMV viral load will be assessed locally if active infection is suspected.

CMV

Suspected CMV infections will be recorded as an infection on the CRF capturing Adverse Events and on the CMV-specific CRF.

CMV-infection is identified by assessments of laboratory and/or clinical sign/symptoms:

- Laboratory-defined CMV (Antigenemia-positive, PCR-positive).
- CMV syndrome (Fever for the last 2 days, neutropenia, leucopenia, viral syndrome).
- CMV disease (Organ involvement).

EBV

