16.2 Appendix 2: Milan criteria

The United Network of Organ Sharing (UNOS) decided to prioritize allocation of organs to those HCC participants who met the tumor criteria recognized in the Milan experience to have the best outcomes (TNM = T2N0). The Milan criteria is based on tumor burden and limit prioritization for OLT to those who have either a single tumor 5 cm or less in diameter with a single hepatocellular carcinoma, and those with no more than 3 nodules, and each 3 cm or less in diameter, without evidence of metastatic disease or vascular invasion. The Milan criteria provide a simple means of selecting participants with HCC for transplantation who are at low risk ($^{10\%}$) for recurrence.

pT0	Tumor not found
pT1	1 nodule ≤ 1.9 cm
pT2	1 nodule 2.0 – 5.0 cm; 2 or 3 nodules, all ≤ 3.0 cm
pT3	1 nodule > 5.0 cm; 2 or 3 nodules, at least one > 3.0 cm
pT4a	4 or more nodules, any size
pT4b	pT2, pT3 or pT4 plus gross intraphepatic portal or hepatic vein involvement as indicated by CT, MRI, or US
N1	Regional (portal hepatitis) nodes, involved
M1	Metastatic disease, including extrahepatic portal or hepatic vein involvement
Stage I	T1
Stage II	T2
Stage III	Т3
Stage IVA1	T4a
Stage IVA2	T4b
Stage IVB	Any N1, any M1

Modified Tumor Node Metastases (pTNM) Classification of HCC

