2.1.3 Subgroup of interest

No subgroup is defined.

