2.2 Participant disposition, demographics and other baseline characteristics

Data for background and demographic variables will be summarized by treatment arm based on the FAS. Continuous variables will be presented with mean, median, 25th percentile, 75th percentile, standard deviation, minimum, maximum, and the number of non-missing observations. Categorical data will be displayed via absolute and relative frequencies for each category (including a category labelled "missing" when appropriate).

The following demographics and baseline characteristics will be reported by treatment arm:

Recipient demographics: age, age group (< 60 years and ≥ 60 years), gender, race (Asian, White, Black or African American, American Indian or Alaska Native, Native Hawaiian or Other Pacific Islander, and Other), height, weight, body mass index (BMI), and region (North America, Europe, and Rest of the world).

- Recipient baseline characteristics: HbA1c level at the time of transplantation, renal function measured by eGFR (MDRD4) (< 30, [30, 55), [55, 70), [70, 90), and ≥ 90 mL/min/1.73m²), diabetic status* (Y/N) prior to transplantation, HCV status (pos/neg), ratio of spot urine protein to creatinine categories**, and evidence and treatment of HCC prior to transplantation (Y/N).
- Donor background information: age, gender, race, weight, allograft weight, donor characteristics (standard criteria donor (SCD), expanded criteria (EXD)), donor category (deceased heart beating, deceased non heart beating), cause of death, ABO blood group/type, RH type, and hypotension prior to procurement (Y/N/unknown).
- Recipient liver transplant background information: end stage disease leading to transplantation, MELD score summary and by-category (≤ 14,[15, 19], [20, 24], [25, 29], and ≥ 30), UNOS classification (Status 1A, Status1B, and Status Non 1), CHILD classification (Status A, Status B, and Status C), and ABO match (Identical and Compatible).
- Recipient and donor viral serology for: CMV, EBV, HCV, HBsAg Anti-Hep B Surface, Anti-Hep B Core, and HIV. CMV donor/recipient constellation (D+R+ / D-R- / D+R- / DR+) is included.
- Liver transplantation procedure information: cold ischemia time summary and by category (≤ 6, (6, 12], and > 12 hours).

* A patient is identified as not having diabetes prior to transplantation if all of the following are true:

- 1. Diabetes was not included in the medical history.
- 2. Glucose (random) < 11.1 mmol/L (200 mg/dL) at the time of transplantation.

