Data collected on AE CRFs will be coded with the MedDRA dictionary that gives preferred term (PT) and system organ class (SOC) information. AEs and infections data will be analyzed as a whole under the heading of AEs for each treatment arm. If a participant has multiple occurrences of an AE, the participant will only be counted once in the corresponding AE category. If participant has multiple AEs within a SOC, the participant will be counted only once for that SOC. If a participant has multiple severity ratings for an AE, the participant will be counted under the maximum rating.

Incidence rates of safety topics of interests from eCRS will be summarized by risk categories. Safety topics of interests are defined in Table 2-2.

Safety topics of interests	Search strategy	
Infections	MedDRA search strategy SOC "Infections and infestations" [10021881] and HLGT "Microbiology and serology investigations" [10027529].	
Malignancies including Lymphoproliferative disorder	SMQ Malignant or unspecified tumours (Narrow) (20000091), SMQ Malignancy related therapeutic and diagnostic procedures (20000093) and SMQ Tumour markers (20000094)	
Thrombosis	MedDRA search strategy SMQ "Embolic and thrombotic events (SMQ)" [20000081] and HLT "Coagulation and bleeding analyses" [10009728].	

 Table 2-2
 Safety topics of interests

Novartis	
SAP	

Immunogenicity	PT: Drug specific antibody present [10013745]		
	SMQ: Hypersensitivity (Narrow), (20000214)		
Vaccination failure	Therapeutic product ineffective (10060769)		
	Therapeutic response changed (10074941)		
	Therapeutic response decreased (10043414)		
	Therapeutic response delayed (10053181)		
	Therapy non-responder (10051082)		
	Antibody test abnormal (10061425)		
	Antibody test negative (10061426)		
	Immunology test abnormal (10061214)		
	Vaccination failure (10046862)		
	Vaccine breakthrough infection (10067923)		
	Absence of immediate treatment response (10081766)		
	Drug effect less than expected (10083365)		

The AE, SAE, infections, and serious infections summarized as above will also be provided in corresponding listings.

New onset of diabetes mellitus (NODM)

New onset diabetes mellitus is defined as:

- a. All of the following should be true (no diabetes pre-transplantation):
 - 1. Diabetes was not included in the medical history.
 - 2. Glucose (random) < 11.1 mmol/L (200 mg/dL) at the time of transplantation.
 - 3. Diabetes was not recorded as reason for any medication given prior to transplantation.

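### SAP Table 2-2 pools recurrence of pre-transplant HCC with new malignancies over the whole safety set, which dilutes the relative risk of new malignancy; two extra rows would fix this cheaply (minor)

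*SAP*

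**What the plan says.** **Who is enrolled.** Protocol 5.2 exempts HCC from the five-year malignancy exclusion (criterion 8). It bars HCC only outside Milan criteria (criterion 9) or with adverse explant pathology (criterion 29). On the Milan criteria, Protocol Appendix 2 says they "provide a simple means of selecting participants with HCC for transplantation who are at low risk" of recurrence, and prints 10% with no time horizon.

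**What is collected.** Protocol 8.4.4 states "All cases of HCC recurrence or de novo HCC, diagnosed post-randomization should be recorded on the appropriate CRF" and also requires an SAE report. The same section makes any malignancy, PTLD included, an SAE. Protocol 8.2 has an HCC form for disease known before transplant or found incidentally around it.

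**What is analysed.** SAP Table 2-2 builds one malignancy topic from three standard queries, two of which are "SMQ Malignant or unspecified tumours (Narrow) (20000091), SMQ Malignancy related therapeutic and diagnostic procedures (20000093"; the third covers tumour markers. On reporting, SAP 2.7 says "Incidence rates of safety topics of interests from eCRS will be summarized by risk categories", and separately "Malignancies are summarized under SAEs". On the population, SAP 2.1.2 says "All safety analyses, including renal function parameters other than GFR, will be performed on the SAF"; SAP 2.1.3 says "No subgroup is defined".

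**What helps a reader.** SAP 2.2 summarizes "evidence and treatment of HCC prior to transplantation (Y/N") by arm and lists baseline characteristics. SAP 2.7 provides SAE listings. Under its disclosure heading it commits to treatment-emergent SAEs by arm, organ class and preferred term.

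Neither SAP 2.7 nor Protocol 12 plans an analysis of HCC recurrence. Protocol 6.3.2 describes no stratification by HCC.

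**The concern.** Recurrence and new malignancy have different populations at risk. Anyone in the safety set can develop a new cancer or PTLD; only a participant who had HCC at transplant can have it recur. One incidence over everyone answers neither question cleanly. It understates recurrence among those at risk. It also adds to each arm a block of events that need not respond to the drug in the same way as new malignancy does, and this pulls the ratio between arms towards 1.

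Protocol 4.6 names lymphoproliferative disorders among the potential risks of CFZ533, in its first study in liver recipients. At these arm sizes only one or two new malignancies per arm would be expected, so the classification of a single case affects how the topic reads.

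The other two queries may widen the mixture. HCC participants are followed with tumour markers and imaging (Protocol 8.4.4), and scheduled alpha-fetoprotein at randomization is for HCC participants only (Protocol Table 8-1, footnote 4). This part cannot be quantified from the documents.

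**Working it through.** The plan states no malignancy rate, so there is no figure of its own to reproduce.

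**Inputs**
- Arm sizes, as planned: 128 randomized 2:3:3 (Protocol 3 and 6.1.3), so 128 × 2/8 = 32 control and 128 × 3/8 = 48 per CFZ533 arm.
- *h*, share with HCC at transplant: not in the documents; assumed 20-50%.
- *r*, on-study recurrence among them: Appendix 2 prints 10% without a time horizon; assumed 5-10%.
- *d*, new-malignancy risk over all participants: not in the documents; assumed 1-2%.

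**1. Dilution, with HCC balanced between arms.** Suppose CFZ533 triples new malignancy and leaves recurrence unchanged. The pooled ratio is (*hr* + 3*d*) / (*hr* + *d*). Expected counts in 48 participants are 48*hr* recurrences and, at the control rate, 48*d* new malignancies.

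| h | r | d | Recurrences in 48 | New in 48 | Pooled ratio (true 3) |
|---|---|---|---|---|---|
| 20% | 5% | 2% | 0.48 | 0.96 | 0.07/0.03 = 2.33 |
| 20% | 10% | 2% | 0.96 | 0.96 | 0.08/0.04 = 2.00 |
| 30% | 10% | 2% | 1.44 | 0.96 | 0.09/0.05 = 1.80 |
| 50% | 10% | 1% | 2.40 | 0.48 | 0.08/0.06 = 1.33 |

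The first and last rows are the ends of the range. With fewer recurrences the dilution eases: *h* = 20%, *r* = 3%, *d* = 3% gives (0.006 + 0.09)/(0.006 + 0.03) = 2.67. In a separate new-malignancy row the expected ratio is 3*d*/*d* = 3.0 in every case.

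The expected risk difference is not diluted. It is 2*d* pooled or split; in the third row, 0.09 − 0.05 = 0.04 pooled and 0.06 − 0.02 = 0.04 split. For the difference, pooling only adds noise.

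**2. Chance imbalance in HCC, 48 against 32.** The 95% range of the difference in HCC share is ±1.96 × √[*h*(1−*h*)(1/48 + 1/32)]:
- *h* = 20%: ±17.9 points
- *h* = 30%: ±20.5 points
- *h* = 40%: ±21.9 points
- *h* = 50%: ±22.4 points

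Multiplied by *r* = 10%, this moves the pooled rate difference by 1.8 to 2.2 points. Across 48 participants that is 48 × 0.018 = 0.9 to 48 × 0.022 = 1.1 participants.

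**3. The same shift against ordinary sampling error.** Take a pooled rate of 30% × 10% + 2% = 5%. The 95% sampling range of a 48 against 32 difference is ±1.96 × √[0.05 × 0.95 × (1/48 + 1/32)] = ±9.7 points. The imbalance in step 2 is small beside this.

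**The case against.** The strongest reply is that the report as a whole already separates most of this.

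- **Tables and listings.** Every malignancy is an SAE, and the disclosure tables show SAEs by arm and preferred term. PTLD and non-liver cancers will therefore appear apart from liver tumours. Baseline HCC is tabulated by arm, and baseline data and SAEs are listed, so a handful of liver cases can be checked one by one. This stands, and a reader who inferred that nothing in the SAP distinguishes these outcomes would be wrong. What remains is that a preferred term need not show whether an HCC is new or recurrent, and none of these tables uses participants with HCC as the denominator.
- **Imbalance.** A reader might infer that uneven HCC between arms could conceal or fabricate a drug signal. The documents do not support this. Under unstratified randomization such imbalance is part of the sampling variance, as for any prognostic factor, and it moves about one participant.
- **Inputs.** A reader might also infer that recurrences will be about as frequent as new cancers. The documents give neither the HCC share nor a new-cancer rate. The printed 10% refers to Milan selection alone. Criterion 29 removes higher-risk explants, the study was terminated early (SAP 1), and AE counting ends 12 to 14 weeks after the last dose (SAP 2.7). On-study recurrence may well be lower.
- **Recurrence as a safety outcome.** Protocol 1.1 lists recurrent as well as de novo cancers among the harms of current immunosuppressants, so a pooled count is legitimate. That argues for keeping the total; an effect on recurrence is still best seen among those who can recur.
- **No decision hangs on it.** The topic is descriptive, the stopping rules use only rejection and serious infection, and the SAP is cut down for an abbreviated report. The case-retrieval strategy behind the risk categories is not in the documents, so it may already sub-classify. These points limit the importance; they do not supply the missing rows.

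**Conclusion.** The point holds as a minor reporting improvement. Table 2-2 pools two outcomes with different populations at risk, and no planned output reports either one over its own denominator. The consequence is dilution of the relative risk: a true threefold increase in new malignancy would show as about 1.3 to 2.3. That range rests on an assumed HCC share of 20-50%, recurrence of 5-10%, new malignancy of 1-2%, no drug effect on recurrence, and the planned 48 and 32 participants. Lower recurrence weakens it, and the expected risk difference is unaffected. Chance HCC imbalance contributes about 2 points at most at 10% recurrence, against a sampling range of about ±9.7 points. It is noise, not bias, and does not itself justify a change. With counts this small, neither the pooled nor the split figures could establish or exclude a malignancy risk. The gain is in interpretability.

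**What to change.** In SAP 2.7 and Table 2-2, keep the pooled malignancy line as a total and add two rows by arm:

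- **(a) New malignancy, including PTLD and de novo HCC**, over all SAF participants.
- **(b) HCC recurrence**, over SAF participants with HCC before transplant or in the explant.

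Identify both the at-risk group and the recurrences from the existing HCC forms (Protocol 8.2 and 8.4.4). The baseline flag in SAP 2.2 should not be used alone, because it describes HCC before transplantation and may miss tumours found incidentally. The SAP already uses a condition-free denominator for new-onset diabetes. The parallel is loose, since new onset is part of that endpoint's definition, but the derivation is of the same kind.

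The cost is a few lines of SAP text, one derived flag and two table rows. No new data and no change to trial conduct are needed. The downside is very small counts: under the assumptions above, about 0.5 to 2.4 recurrences and 0.5 to 1.0 new malignancies (at the control rate) per 48 participants. The rows should be read as counts with denominators, not as a comparison.
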